3. RATIONALE FOR STUDYING DIFFERENT DOSES OF IBRUTINIB IN PATIENTS WITH CLL

Dose of ibrutinib versus clinical response

In a phase I study of ibrutinib in 56 patients with relapsed or refractory B-cell malignancies, BTK occupancy $\geq 95\%$ was achieved 4 hours post-dose in all patients receiving 2.5 mg/kg/day.⁶⁰ Additionally, complete or near-complete BTK occupancy was observed in patients with area under the curve (AUC) exceeding 160 ng x h/ml.⁶⁰ BTK occupancy was measured using a highly specific fluorescent affinity probe, whose binding to the BTK active site had previously been shown to tightly correlate with blockade of BCR signaling and in vivo efficacy.⁹ Dose escalation proceeded up to three dose levels above the level at which full BTK occupancy was observed, i.e., 12.5 mg/kg/day, and all dosing cohorts from 2.5 through 12.5 mg/kg/day had $>95\%$ BTK occupancy and similar response rates.⁶⁰ In the context of clinical observations in patients with CLL that show that patients whose ibrutinib

dose is reduced to 280 mg/d or 140 mg/d because of AEs continue to respond ([name], unpublished observations), these data provide a compelling argument that doses of ibrutinib lower than the approved 420 mg/d will be effective in CLL.

Decrease in off-target effects

Lower doses should result in lower concentrations of free drug in plasma and reduced binding to off-target kinases such as TEC, likely leading to a decreased incidence of AEs such as AF and bleeding manifestations. Acalabrutinib, a new and more selective irreversible BTK inhibitor, does not inhibit other kinases such as EGFR, TEC and ITK at pharmacologically active concentrations.¹² In a phase I/II trial in 61 heavily pretreated patients (median 3 prior therapies, 31% with del17p, 75% with unmutated IgVH), acalabrutinib produced an ORR of 95% (85% PRs, 10% PR-Ls, 100% ORR in patients with del17p) without any major hemorrhage or AF.¹²

Decrease of total BTK in CLL cells during ibrutinib therapy

Prior investigations in murine models demonstrated that BTK protein total levels increased after B-cell receptor pathway stimulation.⁶¹ Similar observations were recently made in an adoptive transfer CLL murine model.⁶² The mechanism involved the CXCR4-CXCL12 signaling pathway. As a corollary, inhibition of BTK by ibrutinib in murine model resulted in a decline in total BTK along with internalization of CXCR4 receptors.

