6.2 Treatment plan

Patients will receive ibrutinib orally daily for 3 cycles. Cycles will be 28 days long. Ibrutinib will be administered continuously, at approximately the same time each day, without regard to food. In the first cycle, the daily dose of ibrutinib will be 420 mg (3 capsules), in the second cycle, 280 mg (2 capsules) and in the third cycle, 140 mg (1 capsule). Patients will swallow the ibrutinib capsules whole with water without opening, breaking or chewing them.

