8 EVALUATION DURING STUDY

- 8.1 Physical examination along with evaluation of performance status, recording of AEs and concomitant medications on day 28 (± 2 days) of each cycle.
- 8.2 CBC and differential on day 28 (± 2 days) of each cycle.
- 8.3 Albumin, alkaline phosphatase, total, direct and indirect bilirubin, bicarbonate, BUN, calcium, chloride, creatinine, glucose, LDH, phosphorus, potassium, total protein, SGPT (ALT), SGOT (AST), and sodium on day 28 (± 2 days) of each cycle.
- 8.4 Serum beta-2-microglobulin and immunoglobulin levels (IgG, IgA, IgM) on day 28 (± 2 days) of each cycle.
- 8.5 ECG on day 28 (± 2 days) of each cycle.
- 8.6 Plasma concentrations of ibrutinib by high performance liquid chromatography with tandem mass spectrometric detection as previously described,⁶⁰ just before dosing and at 4 and 24 hours post-dosing on days 1, 8, and 28 (but before the first dose of the next cycle) of each cycle. Exception: there will be no 4-hour blood draw on day 28. Chemokines will also be measured, using enzyme-linked immunosorbent assay (ELISA).
- 8.7 BTK occupancy level by fluorescent affinity probe detection as previously described,^{9, 60} just before dosing and at 4 and 24 hours post-dosing on days 1, 8, and 28 (but before the first dose of the next cycle) of each cycle. Exception: there will be no 4-hour blood draw on day 28. See section 8.11.
- 8.8 Measurement of BTK mRNA and BTK and phospho-BTK protein and downstream signaling, as previously described,^{74, 75} just before dosing and at 4 and 24 hours post-dosing on days 1, 8, and 28 (but before the first dose of the next cycle) of each cycle. Exception: there will be no 4-hour blood draw on day 28.
- 8.9 Quantification of NF- κ B activation by ELISA as previously described,⁷⁶ just before dosing and at 4 and 24 hours post-dosing on days 1, 8, and 28 (but before the first dose of the next cycle) of each cycle. Exception: there will be no 4-hour blood draw on day 28.
- 8.10 Measurement of platelet functionality as previously described,⁷⁷ just before dosing and at 24 hours post-dosing on days 1 and 28 (but before the first dose of the next cycle) of each cycle.
- 8.11 Peripheral blood samples for plasma ibrutinib and cytokine levels, BTK occupancy, total and phospho-BTK mRNA and protein levels as well as levels of other downstream mediators of BCR signaling, and NF- κ B activity (appendix C) will be sent for processing to the laboratory of [name], Ph.D. at:

[name]
 [name]

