Appendix B. Reporting requirements.

These guidelines will be followed for the recording and reporting of adverse and serious adverse events.

1. Baseline events will be recorded in the medical history section of the case report form and will include the terminology event name, grade and start date of the event.
 - a. Baseline events are any medical condition, symptom, or clinically significant lab abnormality present before the informed consent is signed.
 - i. Hematologic laboratory abnormalities will not be recorded as baseline events for patients with acute leukemia, myelodysplastic syndrome, chronic lymphocytic leukemia, or chronic myeloid leukemia in blast phase.
 - ii. If exact start date is unknown, month and year or year may be used as the start date of the baseline event.
2. The maximum grade of the adverse event will be captured per course of protocol defined visit date.
3. These adverse events will be recorded in the case report form:
 - a. Any grade adverse event that is possibly, probably or definitely related to the study drug(s).
 - b. All serious adverse events regardless of attribution to the study drug(s).
 - c. Any grade adverse event regardless of attribution to the study drug(s) that results in any dose modification.
4. Hematologic adverse events will not be recorded or reported for studies in patients with acute leukemia, myelodysplastic syndrome, chronic lymphocytic leukemia, or chronic myeloid leukemia in blast phase except for:
 - a. Prolonged myelosuppression as defined by the NCI-CTCAE criteria specific for leukemia, e.g., marrow hypocellularity on day 42 or later (6 weeks) from start of therapy without evidence of leukemia (<5% blasts), or that results in dose modifications, interruptions or meets the protocol definition of dose limiting toxicity (DLT) or serious adverse event (SAE).
5. Serious adverse events will be reported according to institutional policy.
6. Protocol specific language regarding the recording and reporting of adverse and serious adverse events will be followed in the event of discordance between the protocol and Leukemic-specific adverse event recording and reporting guidelines.

Serious Adverse Event Reporting (SAE) for M. D. Anderson-Sponsored Protocols

An adverse event or suspected adverse reaction is considered “serious” if, in the view of either the investigator or the sponsor, it results in any of the following outcomes:

- Death

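### Non-serious adverse events that change no dose are recorded only if judged at least possibly drug-related, by someone who knows the dose, so the descriptive safety-by-dose comparison is open to attribution bias

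*Combined protocol and SAP*

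**What the plan says.** Section 12 refers all reporting to Appendix B. Item 3 there names three routes into the case report form: "Any grade adverse event that is possibly, probably or definitely related to the study drug(s" (3a); "All serious adverse events regardless of attribution to the study drug(s" (3b); and "Any grade adverse event regardless of attribution to the study drug(s) that results in any dose modification" (3c). Item 4 is a separate restriction: "Hematologic adverse events will not be recorded or reported for studies in patients with acute leukemia, myelodysplastic syndrome, chronic lymphocytic leukemia" and other leukemia groups, with listed exceptions. Item 6 sets the order of precedence: "Protocol specific language regarding the recording and reporting of adverse and serious adverse events will be followed in the event of discordance" with the departmental guidelines.

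In the protocol body, Section 8.1 asks for "recording of AEs and concomitant medications on day 28" of each cycle, and the study calendar shows adverse event evaluation running through treatment. Neither says whether every event is captured or only those that item 3 admits.

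Section 6.2 fixes the dose sequence: "In the first cycle, the daily dose of ibrutinib will be 420 mg (3 capsules), in the second cycle, 280 mg (2 capsules", followed by 140 mg (1 capsule) in the third. Section 3 expects lower doses to reduce off-target binding, "likely leading to a decreased incidence of AEs such as AF and bleeding manifestations". Section 1.1.2 makes safety at the three doses part of the secondary objective, and Section 11 plans descriptive statistics only.

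**The concern.** For non-serious events that change no dose, the causality judgement decides whether the event exists in the data at all. It is made by someone who can see the dose, in a protocol that states which way toxicity should move as the dose falls. If that knowledge makes an assessor readier to call an event possibly related at 420 mg than at 140 mg, recorded events will fall with dose even where true events do not. Because the rejected events were never entered, no later analysis can restore them or test whether attribution drifted. At stake is how far the safety-by-dose tables can be read as describing toxicity rather than opinion about toxicity.

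**Working it through.** There is no planned figure to reproduce. The check is a reading of the rules, followed by one line of algebra on size.

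1. **Which events the filter touches.** Under Appendix B, item 3:
   - serious: recorded whatever the attribution (3b);
   - non-serious, dose modified: recorded whatever the attribution (3c);
   - non-serious, no dose modification, at least possibly related: recorded (3a);
   - non-serious, no dose modification, judged unrelated: not recorded.

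   Only the last two classes depend on attribution. Most hematologic events are already removed by item 4, even when drug-related, so the exposed class is essentially non-hematologic.

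2. **Which grades.** Section 6.3 calls for interruption at grade 3 or above for non-hematologic toxicity. If an interruption counts as a dose modification, those events enter through 3c. Section 6.3 treats interruption under its dose-modification heading, whereas item 4 lists modifications and interruptions as separate things, so this is likely but not explicit. What remains is mainly grade 1-2. That is not a marginal class: Section 2.3 describes the adverse events in the two registration trials as mostly of those grades.

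3. **Is the dose known?** The documents do not use the term open-label and do not say who attributes. But every patient follows the same descending capsule count (Sections 6.2 and 11), supply is commercial (Section 4.5), and no masking is described. Knowledge of the dose follows.

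4. **Is a direction expected?** Yes. Section 3 predicts fewer events at lower doses, and Section 11 says that prior experience shows lower toxicity below the standard dose.

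5. **Does Section 8.1 already override item 3?** Item 6 lets protocol language prevail only where the two conflict. Section 8.1 asks that events be recorded without saying which, so it can be read consistently with item 3. The override is not clear.

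6. **Size.** For the exposed class at dose d, let p(d) be the true event rate and a(d) the probability of being judged at least possibly related. The expected recorded rate is p(d) × a(d), so

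   recorded ratio, 140 mg to 420 mg = [p(140)/p(420)] × [a(140)/a(420)].

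   With no true dose effect, p(140) = p(420) and the ratio reduces to a(140)/a(420). If attribution is the same at both doses the ratio is 1 and there is no bias. The documents give neither a(140) nor a(420), so any percentage quoted would only restate an assumption. The any-grade bleeding proportion in Section 4.9 (about half of patients) does not help: it cancels from the ratio, and it is a proportion of treated patients with no stated period, not a rate per 28-day cycle.

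**The case against.** The case for leaving the rule alone has several parts.

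- **The threshold is low.** Bruising and diarrhea appear in the protocol's own background as known effects of the drug. An assessor would rarely rule out even a possible relation for them, at any dose. This stands and limits the likely size.
- **The important events are protected.** Serious and dose-modifying events are kept, and ECG and chemistry are done on day 28 of each cycle whatever the attribution. This stands and confines the point to low-grade events.
- **The comparison is modest.** Safety is secondary and descriptive, with no test or decision rule on event counts by dose. This stands.
- **Recording everything does not rescue the comparison.** Dose falls in the same order in every patient, and Section 2.4 says that bleeding risk appears to fall with continued therapy. Staff and patients who know the dose may also differ in how they elicit, report and grade events. This stands too: the change removes one source of bias, not all of them.

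None of this shows that the filter is harmless or needed. Attribution can be kept as a field without being a condition of entry.

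A reader might infer that a falling event count in this trial would be produced by attribution. The documents do not support that. They show that the route is open, not that assessors take it, and true dose effects and time on treatment could give the same pattern.

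**Conclusion.** The point holds as a limited one. Appendix B, item 3, puts a judgement made with the dose known between the patient and the safety-by-dose tables, and Section 8.1 does not clearly lift it. The exposed part is mainly non-serious grade 1-2 non-hematologic events. Bias towards fewer recorded events at the lower doses is plausible given the protocol's stated expectation, but it is not demonstrated, and its size cannot be derived from the documents.

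The conclusion rests on two inferences: that whoever attributes knows the dose, which follows from the fixed capsule schedule, and that Section 8.1 is not meant to require every event. If the sponsor does mean Section 8.1 that way, the text still needs to say so.

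A reader might also infer that the trial's safety data as a whole, or its main result, are compromised. They are not: serious and dose-modifying events do not pass through the filter, and the primary BTK occupancy analysis does not use adverse event records. This is a cheap improvement worth making.

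**What to change.** In Section 8.1, state as protocol-specific language that prevails under Appendix B, item 6, that all non-hematologic adverse events of any grade are recorded regardless of attribution. Record attribution as a separate field, with the onset date and the dose being taken at onset. The dose field is needed because item 2 captures the maximum grade per course, while Section 6.3 allows reductions that make the dose taken differ from the dose planned for the cycle.

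Say explicitly whether the hematologic exclusion in item 4 stays. CBC values are collected on day 28 of each cycle (Section 8.2) in any case, so blood counts by cycle remain available if it does.

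In Section 11, tabulate all-cause events first, by cycle and by dose taken, and related events second. Add a note that dose remains confounded with time on treatment, so neither table isolates a dose effect.

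The cost is a small number of extra case report form entries for 12 patients over 12 weeks (3 × 28 = 84 days). No visit, sample or primary analysis changes.

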1.2 Endpoints

- 1.2.1 Primary: Ibrutinib plasma and chemokine concentrations, BTK occupancy by ibrutinib, BTK mRNA levels, BTK phospho- and total protein levels, downstream signaling, NF- κ B p65 levels and platelet functionality on days 1 (baseline), 8 and 28 of each cycle of treatment.
- 1.2.2 Secondary: Absolute lymphocyte count (ALC), hemoglobin and platelet levels, CLL-related symptoms, and palpable lymphadenopathy and/or hepatosplenomegaly on day 28 of each cycle of treatment; characterization of safety and tolerability of ibrutinib throughout the study.

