4.9 Warnings and precautions

Hemorrhage:

Fatal bleeding events have occurred in patients treated with ibrutinib. Grade ≥ 3 bleeding events (subdural hematoma, gastrointestinal bleeding, hematuria and post procedural hemorrhage) have occurred in up to 6% of patients. Bleeding events of any grade, including bruising and petechiae, occurred in approximately half of patients treated with ibrutinib. The mechanism for the bleeding events is not well understood. Ibrutinib may increase the risk of hemorrhage in patients receiving antiplatelet or anticoagulant therapies. Based on the risk-benefit ratio, ibrutinib is suggested to be withheld for at least 3 to 7 days pre- and post-surgery depending upon the type of surgery and the risk of bleeding.

Infections:

Fatal and non-fatal infections have occurred with ibrutinib therapy. Grade ≥ 3 infections occurred in 14% to 26% of patients. Cases of progressive multifocal leukoencephalopathy (PML) have occurred in patients treated with ibrutinib. Patients should be monitored for fever and infections and evaluated promptly.

Cytopenias:

Treatment-emergent Grade 3 or 4 cytopenias including neutropenia (range, 19 to 29%), thrombocytopenia (range, 5 to 17%), and anemia (range, 0 to 9%) occurred in patients treated with ibrutinib. Complete blood counts (CBCs) should be monitored monthly.

Atrial Fibrillation:

Atrial fibrillation and atrial flutter (range, 6 to 9%) have occurred in patients treated with ibrutinib, particularly in patients with cardiac risk factors, acute infections, and a previous history of atrial fibrillation. Patients should be clinically monitored periodically for atrial fibrillation. Patients who develop arrhythmic symptoms (e.g., palpitations, lightheadedness) or new onset dyspnea should have an electrocardiogram (ECG) performed. If atrial fibrillation persists, the risks and benefits of treatment and dose modification should be considered.

Second Primary Malignancies:

Other malignancies (range, 5 to 14%) including non-skin carcinomas (range, 1 to 3%) have occurred in patients treated with ibrutinib. The most frequent second primary malignancy was non-melanoma skin cancer (4 to 11 %).

Tumor Lysis Syndrome (TLS):

TLS has been reported with ibrutinib therapy. Patients should be monitored closely and appropriate precautions taken in patients at risk for TLS (e.g. high tumor burden).

Embryo-Fetal Toxicity:

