6.3 Dose modifications

Ibrutinib therapy should be interrupted for any grade ≥ 3 non-hematologic toxicity, grade ≥ 3 neutropenia with infection or fever, or grade 4 hematologic toxicity, as assessed by the National Cancer Institute Common Terminology Criteria for Adverse Events (NCI CTCAE, version 4.03). Ibrutinib may be resumed at the starting dose for that particular cycle once the toxicity has resolved to grade ≤ 1 or baseline. If the toxicity recurs, the dose should be reduced by 1 capsule (140 mg) daily if this occurs within the first or second cycles. A second reduction of dose by 1 capsule (140 mg) daily may be made for patients in their first cycle of treatment. For patients already taking 1 capsule (140 mg) daily at the time of occurrence of the toxicity (i.e., patients in their third cycle of therapy or second cycle patients after a first dose reduction), therapy with ibrutinib should be discontinued.

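### Cytopenias that neither change dosing nor count as serious or prolonged stay out of the AE record, and no grading of the collected blood counts is planned in their place

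*Combined protocol and SAP*

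**What the plan says.** **Objective and endpoints.** Section 1.1.2 makes the clinical effects of the three doses, safety included, a secondary objective. Section 1.2.2 turns this into two parts. One is a list of day-28 measures: "Absolute lymphocyte count (ALC), hemoglobin and platelet levels, CLL-related symptoms, and palpable lymphadenopathy and/or hepatosplenomegaly on day 28 of each cycle of treatment". The other is "characterization of safety and tolerability of ibrutinib throughout the study". Neutrophils are not named.

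**Recording rule.** Appendix B, item 4: "Hematologic adverse events will not be recorded or reported for studies in patients with acute leukemia, myelodysplastic syndrome, chronic lymphocytic leukemia". The sentence goes on to exceptions. Item 4.a keeps prolonged myelosuppression, "or that results in dose modifications, interruptions or meets the protocol definition of dose limiting toxicity (DLT) or serious adverse event (SAE"). At baseline, item 1.a.i applies the same approach to CLL: "Hematologic laboratory abnormalities will not be recorded as baseline events". Section 12 has no reporting text of its own and only points to Appendix B.

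**Events that interrupt dosing.** Among hematologic events, Section 6.3 names "grade ≥ 3 neutropenia with infection or fever, or grade 4 hematologic toxicity", graded by CTCAE version 4.03.

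**Data collected.** Section 7.2 requires a CBC with differential in the week before treatment. Section 8.2 requires "CBC and differential on day 28 (± 2 days) of each cycle".

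**Analysis.** Section 11 calls for descriptive statistics. Continuous variables, with CBC parameters given as an example, are summarized by means with SDs, medians with ranges, or both. It mentions neither toxicity grades of laboratory values nor change from baseline.

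**The concern.** The plan wants to describe safety at each dose, and its rationale (Section 3) expects fewer AEs at lower doses. Yet a standing rule keeps a defined group of cytopenias out of the AE record, and the analysis section does not recover them from the blood counts. Neutropenia has the highest grade 3-4 rate of the three cytopenias quoted in Section 4.9, and it is the lineage missing from the named endpoints.

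The risk is one of interpretation. A reader of the AE tables who sees few cytopenias at 280 or 140 mg may take this as evidence of hematologic tolerability, when part of it reflects what was written down. The counts that would correct the impression are already in the database.

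**Working it through.** **1. Which cytopenias reach the AE record.** The plan gives no figure of its own on this point, so the first check is to read Appendix B, item 4, against Section 6.3.

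| Event | Recorded as an AE? | Reason |
|---|---|---|
| Any grade 4 hematologic toxicity | Yes | Section 6.3 interrupts dosing; item 4.a exception applies |
| Neutropenia of grade 3 or above with infection or fever | Yes | Same |
| Any cytopenia that is an SAE or changes dosing | Yes | Item 4.a; consistent with items 3.b and 3.c |
| Uncomplicated grade 3 neutropenia | Generally no | No Section 6.3 trigger |
| Grade 3 anemia or thrombocytopenia | Generally no | No Section 6.3 trigger named for hematologic events below grade 4, apart from neutropenia |
| Grade 1-2 cytopenia of any lineage | Generally no | No Section 6.3 trigger |

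Generally no means not recorded unless another exception is met. The prolonged-myelosuppression exception is unlikely to add many events. Its example rests on marrow hypocellularity at day 42 or later, and Section 8 schedules no marrow examination.

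**2. Whether other text overrides item 4.** Item 6 gives precedence to protocol-specific language, but the body contains no contrary rule on recording hematologic AEs. Item 3.a asks for any-grade related AEs, but item 4 is the more specific provision and names CLL. Item 4 therefore stands.

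**3. What Section 11 would report instead.** A mean across 12 patients can hide two or three low counts. A range shows the single lowest value, not how many patients reached a grade or who worsened. Baseline matters here: Section 5.1.5 sets limits for bilirubin, transaminases and creatinine clearance but none for neutrophils, hemoglobin or platelets, so patients may enter with cytopenias that item 1.a.i leaves out of the baseline record.

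**4. Scale.** Inputs: n = 12 (Section 11) and the Section 4.9 rates, given as "Treatment-emergent Grade 3 or 4 cytopenias including neutropenia (range, 19 to 29" percent, with 5-17% for thrombocytopenia and 0-9% for anemia. Expected patients = 12 × p; chance of at least one = 1 − (1 − p)^12.

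| Grade 3-4 event | Expected patients | Chance of at least one |
|---|---|---|
| Neutropenia | 12 × 0.19 = 2.3 to 12 × 0.29 = 3.5 | 1 − 0.81^12 = 92% to 1 − 0.71^12 = 98% |
| Thrombocytopenia | 12 × 0.05 = 0.6 to 12 × 0.17 = 2.0 | 1 − 0.95^12 = 46% to 1 − 0.83^12 = 89% |
| Anemia | 0 to 12 × 0.09 = 1.1 | 0% to 1 − 0.91^12 = 68% |

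These count all grade 3-4 events, recorded or not. If a share g of the neutropenia is uncomplicated grade 3 that meets no exception, the number missed is 12 × p × g. The documents do not split grade 3 from grade 4 and do not give g. Over g from 0 to 1, the number missed runs from 0 to 2.3 at p = 0.19 and from 0 to 3.5 at p = 0.29. Grade 1-2 events cannot be sized at all, because no rate is quoted.

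**The case against.** The strongest reply is that little is lost. The exceptions keep the severe events that matter most for management. Hemoglobin and platelets are named day-28 endpoints in each cycle. Section 11 covers CBC parameters, and since the CBC includes a differential, that wording can reach neutrophils; with 12 patients, the bottom of a range would reveal a very low count. Cytopenia is often part of CLL itself, which is a plausible reason for item 4. Safety is a descriptive secondary aim in a pilot built around pharmacology.

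Much of this stands. The data are collected, and values will be summarized for at least two of the three lineages. What is missing is graded incidence and change from baseline, together with an explicit commitment on neutrophils. Disease-related cytopenia is an argument for showing shifts from baseline; it does not justify leaving grades out.

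A second reply also stands. Every patient takes 420, then 280, then 140 mg (Section 6.2), so dose cannot be separated from time on treatment, and Section 2.3 reports that grade 3 or higher cytopenias became less frequent with longer follow-up. The scheduled on-treatment CBC falls only on day 28, and growth factors are permitted (Section 6.7). Better tabulation will not turn these data into a clean dose comparison.

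**Conclusion.** The point holds in a limited form. The AE tables will understate cytopenias by rule, and no planned analysis reports how many patients reached each grade or worsened from baseline in each cycle. The primary objective is unaffected. The change is worth making because it improves a stated secondary objective at almost no cost.

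Three stronger readings are tempting, and the documents do not support them:

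- **Hematologic AEs go unrecorded altogether, or the tables would show almost no neutropenia.** The exceptions capture all grade 4 events and infected or febrile neutropenia of grade 3 or above. Whether most cytopenias are missed cannot be shown without a split by grade.
- **Some 2.3-3.5 patients with severe neutropenia would be missed.** That range is the expected number with any grade 3-4 neutropenia, including those the plan records. It also assumes that the Section 4.9 rates apply to 12 weeks of treatment; they may come from longer follow-up, so it is best treated as an upper figure.
- **The recording rule hides a dose effect.** The fixed dose order and the few expected events would prevent a clear conclusion about dose even with complete recording.

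**What to change.** 1. In Section 1.2.2, add absolute neutrophil count to the day-28 counts.
2. In Section 11, state that CTCAE version 4.03 grades for neutrophils, hemoglobin and platelets will be derived from the pretreatment and day-28 CBCs, plus any unscheduled CBCs available, whether or not an AE was recorded.
3. Tabulate these grades per cycle as shifts from baseline, showing the dose actually taken, since Section 6.3 allows reductions within a cycle.
4. State beside the tables that they are descriptive, that day-28 values can miss lower counts in mid-cycle, and that dose is confounded with time on treatment.

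Appendix B, item 4, can stay as it is. The cost is a little more analysis, with no extra sampling, no new case report form pages and no change to clinical management.
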